### 7.2 Analysis details

Analyses described below represent our planned analyses assuming statistical assumptions are met. If assumptions are not met, we will run alternative tests appropriate for the outcome distribution (e.g., non-parametric tests).

The analyses will be conducted based on the principle of intention-to-treat (ITT). All patients who met the inclusion criteria will be included in the analyses in the arms to which they were assigned. Likewise, all clinicians will be included in analysis in their assigned education arms, regardless of whether they attended their education sessions. Because exposure to pharmacists is dependent upon action by a clinician to refer, we will also conduct a per protocol sensitivity analysis for patients who were consulted to pharmacist care and those patients seen by the pharmacist.

Two-tailed p-values  $< 0.05$  will be used to determine statistical significance in all analyses.

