- Interventions – We will implement the following interventions: 1) focused education through a series of focused in-person or virtual sessions (randomized to receive early or late education); 2) multi-pronged clinical decision support (CDS) inclusive of a patient portal message, an interruptive advisory upon chart entry notifying clinicians to consider GDMT, and a Best Practice Advisory (BPA) that opens a GDMT order set; and 3) the same CDS as #2 but replacing the GDMT order set with a referral to integrated clinical pharmacist co-management.
- Control – Patients seen by clinicians randomized to usual care will be labeled as control patients and receive care as per usual standard practice, which may also include referral to Medication Therapy Disease Management (MTDM).

- Outcomes – The primary outcome will be whether or not improvements in GDMT prescribing occur within 30 days of index date. Additional outcomes will include the primary outcome at 60 and 90 days, GDMT changes at 30, 60 and 90 days, healthcare resource utilization, and total costs of care.
- Data analysis – Analyses are described in detail below. Primary analyses will assess whether outcomes improve between each interventional arm versus control.

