**3. Multiprong CDS with referral to pharmacist co-management (CDS-MTDM), including:**

- A patient-directed questionnaire administered as above in the multi-prong CDS intervention.
- A clinician-facing “Heads-Up” BPA that fires upon initial launch of the encounter in Epic. The BPA notifies the clinician of the patient’s diagnosis of HFrEF and encourages referral to pharmacy for co-management. Patient responses to the pre-visit questionnaire are provided in alternate color font if completed as affirmative by the patient. See Figures 5 and 6 below.

**Figure 5.** Provider-facing EHR alert upon entry into patient chart (without portal information).

[figure not shown]

**Figure 6.** Provider-facing EHR alert upon entry into patient chart (without portal information).

- c. A BPA during the encounter that presents information exactly as in the GDMT order set version described above. The preferred action within the BPA is to refer patients to embedded pharmacist co-management, which is already highlighted for the clinician with an urgent referral sent to pharmacy. Pharmacists are expected to schedule patients within 3 days and meet with patients and optimize GDMT through a CPA. If this option is not selected, the clinician must document their reason for not selecting referral in the acknowledgement section of the BPA. This section included one option for patient declining treatment (will manage Rx on their own), and an “other” category (with required open text response). See Figure 7 below.

**Figure 7.** Provider-facing EHR alert upon order entry for pharmacist referral and co-management.

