## 7. STATISTICAL ANALYSIS PLAN

### 7.1 Power analysis

Data will be collected from 4,300 patients assigned to the clinicians in the study. With CDS-OS and CDS-MTDM (versus control), we expect to have 80% power to detect approximately 5 and 9 percentage-point increases, respectively, in prescribing GDMT within 30 days, at two-tailed  $p < .05$  with robust standard errors clustered at the clinician level. With education versus delayed education, we expect to have 80% power to detect an approximately 5.5 percentage-point increase in prescribing GDMT, with robust standard errors clustered at the clinician level. Power analyses were conducted using DeclareDesign.

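### The planned per-protocol analysis selects patients on referral to, or contact with, a pharmacist after randomisation, with no comparator or adjustment stated, so it cannot test the robustness of the ITT result

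*Combined protocol and SAP*

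**What the plan says.** Section 7.2 makes ITT the governing principle: "All patients who met the inclusion criteria will be included in the analyses in the arms to which they were assigned". It then gives a reason for a further analysis, "Because exposure to pharmacists is dependent upon action by a clinician to refer", and plans a "per protocol sensitivity analysis for patients who were consulted to pharmacist care and those patients seen by the pharmacist". The two-tailed 0.05 threshold "will be used to determine statistical significance in all analyses", so this analysis would receive a significance verdict too.

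Section 7.2 does not say:
- who the comparator is;
- whether referred control or CDS-OS patients count;
- when the referral or visit must fall relative to the 30-day outcome;
- how selection will be handled.

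Section 7.2.2 defines the planned test for each active CDS arm as a comparison with the control arm.

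Other sections bear on who is selected:
- **Section 6.7, CDS-MTDM.** Referral is the pre-highlighted action, and a clinician who does not refer must record why. Of those acknowledgements the plan says: "This section included one option for patient declining treatment". Pharmacists are expected to schedule patients within 3 days and then optimise GDMT themselves.
- **Sections 3 and 6.7, Control.** Control clinicians may also use pharmacist services.
- **Section 6.2.** Randomisation was stratified partly on MTDM referral history, because prescribing was expected to differ with it.
- **Section 10.** Referral rates in the CDS-MTDM arm were monitored. As an example, clinicians below 50% in February 2024 were contacted.

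**The concern.** Randomisation makes the whole CDS-MTDM arm comparable with the whole control arm. It does not make the referred part of one arm comparable with all of the other. Referral depends on the clinician. Being seen depends on scheduling and on the patient attending. Some patients who decline treatment leave the selected set through the acknowledgement, while similar controls stay in if all controls are the comparator. Selection also weights an arm holding about 10% of clinicians towards its high referrers, which undoes part of the balance that stratifying on referral history was meant to secure.

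The plan accepts this principle elsewhere. Section 7.2.2 adjusts the education comparison for covariates, including baseline prescribing, because education was not randomly assigned. Referral is not randomly assigned either, yet no adjustment is attached to it.

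At stake is interpretation. A sensitivity analysis is normally read as a check on whether the main result stands. This one answers a different question with an unprotected comparison, in the smallest arm, where ITT is least precise. Agreement with ITT would not confirm it and disagreement would not undermine it.

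**Working it through.** **1. The plan's own figure.** The plan gives no figure for this analysis. The nearest yardstick is the ITT detectable difference in section 7.1: "approximately 5 and 9 percentage-point increases, respectively, in prescribing GDMT within 30 days" at 80% power, for CDS-OS and CDS-MTDM against control. The control rate and ICC are not stated, so it cannot be strictly reproduced, but it is attainable.

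Inputs:
- 4,300 patients (section 7.1).
- A 45/45/10 split (section 6.1), giving about 1,935 / 1,935 / 430 patients if patients divide as clinicians do (assumption).
- 103 current clinicians (section 6.2), so m = 4,300/103 = 41.7 patients each.
- Control rate 20% and ICC 0.02 to 0.03 (assumptions).

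The design effect is 1 + (m − 1) × ICC:
- ICC 0.02: 1 + 40.7 × 0.02 = 1.81.
- ICC 0.03: 1 + 40.7 × 0.03 = 2.22.

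Dividing the sample sizes by these and solving a two-sided 0.05 two-proportion test for 80% power gives 5.1 to 5.6 points (CDS-OS) and 8.5 to 9.4 points (CDS-MTDM). The 9 points apply to the whole arm under ITT and serve below only as a scale.

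**2. Bias when assignment to CDS-MTDM changes nobody's outcome.** Let p1 and p0 be the 30-day increase rates in referred and non-referred patients, r the share referred, and g = p1 − p0. The arm rate is p = r·p1 + (1 − r)·p0. With no effect of assignment this equals the control rate, so

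referred CDS-MTDM minus all controls = p1 − p = (1 − r) × g.

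With rate ratio RR = p1/p0, p0 = p / (r·RR + 1 − r) and p1 = RR × p0.

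**3. Numbers.** All of p = 20%, r = 50% and RR are assumptions. The last column comes from a clustered simulation with no true effect (46 control and 10 CDS-MTDM clinicians, ICC 0.02, cluster-robust variance with Satterthwaite t, 800 runs per setting).

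| RR | p0 | p1 | g (points) | Bias (1 − r) × g (points) | Significant at 0.05 |
|---|---|---|---|---|---|
| 0.67 | 24.0% | 16.0% | −7.9 | −4.0 | 23% (towards harm) |
| 1 | 20.0% | 20.0% | 0 | 0 | 5% |
| 1.5 | 16.0% | 24.0% | +8.0 | +4.0 | 13% |
| 2 | 13.3% | 26.7% | +13.3 | +6.7 | 27% |
| 3 | 10.0% | 30.0% | +20.0 | +10.0 | 59% |

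Example, RR = 2: p0 = 0.20 / (0.5 × 2 + 0.5) = 0.133; p1 = 0.267; bias = 0.5 × 0.133 = 0.067.

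**4. Range.** Over p = 20 to 30%, r = 30 to 70% and RR = 0.67 to 3, the bias runs from −7.7 points (p = 30%, r = 30%, RR = 0.67) to +26.3 points (p = 30%, r = 30%, RR = 3).

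**5. Two checks from the same simulations.**
- ITT showed a mean difference of about 0 and rejected in about 4 to 7% of runs in every setting.
- Referred CDS-MTDM against referred controls, with an identical referral process in both arms, also gave about 0 and rejected in about 4 to 7% of runs.

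**The case against.** The strongest reply is that the direction and size of the bias are not in the documents. A reader might infer that this analysis must show a benefit for an inert intervention. That inference needs two things: all controls as comparator, and referred patients who are more likely to have a GDMT increase anyway. Section 7.2 names no comparator, and nothing quantifies the second condition. The bias vanishes at RR = 1 and reverses below it. The acknowledgement text also cuts both ways: the decline option carries a parenthesis about managing the prescription on their own, and if that means prescribing continues without the pharmacist, some non-referred patients may still have an increase. Clinicians could also refer harder-to-treat patients. All of this stands, and it rules out a claim of certain benefit.

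A second reply is that the comparator might be referred controls, for whom the simulated bias was about zero. That result assumes the same referral process in both arms. Here the processes differ by design: CDS-MTDM pre-highlights referral and follows up low referrers, while controls refer as usual. The reply therefore does not settle the matter, and an unnamed comparator can be chosen after the data are seen.

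Third, ITT governs, the analysis is secondary, and no section says it will support or qualify the ITT finding. Table 3 already plans the percentages referred and seen, and section 7.2.2 already plans sensitivity models with clinician baseline prescribing, though not expressly for this subset. This stands and limits the seriousness. It does not make the analysis a robustness check, because a contrast whose bias may take either sign cannot serve as one.

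**Conclusion.** The point holds in a limited form. The subset is defined by post-randomisation events, with no comparator, window or adjustment stated. Against all controls, which is the natural but unstated reading of section 7.2.2, it could show a benefit or a harm with no true effect.

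At the assumed 20% rate and 50% referred, the bias is between −4 and +10 points for rate ratios of 0.67 to 3, and only the top of that range exceeds the 9 points stated for the whole arm. Upward bias looks more plausible, since some decliners are removed, being seen requires attendance, and pharmacists change GDMT themselves. The documents do not establish it. The ITT conclusion is unaffected, so this is an inexpensive improvement to a secondary analysis and not a threat to the primary result.

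**What to change.** In section 7.2, drop the per-protocol sensitivity label and replace the sentence with text to this effect:

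> ITT is the only basis for the effectiveness claim. Within CDS-MTDM, 30-day outcome rates will be described by uptake (referred or not, seen or not), alongside the uptake percentages in Table 3.

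If a contrast with control is kept, the SAP should:
- label it observational and supplementary;
- name the comparator, including how referred controls are treated;
- state the window for referral and visit relative to the 30-day outcome;
- adjust for patient baseline GDMT class use, clinician baseline prescribing and clinician MTDM referral history;
- state that it will not be used to support or qualify the ITT result.

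The baseline data should already be available: class use determines eligibility (section 6.6), clinician prescribing rates are listed as covariates in section 7.2.2, and referral history was a stratification factor (section 6.2). Section 10 reports that outcomes had not been examined by arm beyond a limited alert check. If that is still so, the change can be made without knowledge of results.

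The cost is a wording change, a little more analysis work, and a less prominent estimate of effect in those seen.

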#### 7.2.1 Descriptive statistics

Descriptive statistics will be computed for baseline socioeconomic and demographic characteristics (i.e., sex, age, race, ethnicity, insurance, etc.), including broken out across study arms, with differences compared using the appropriate statistical tests: two-tailed Student's t-tests will be used for continuous data, column proportion z tests or  $\chi^2$  for categorical data, and Mann-Whitney for non-normal quantitative data.

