### 3. ABSTRACT

#### GREAT- HF Care

- Background and Rationale - Heart failure with reduced Ejection Fraction (HFrEF) is associated with high mortality and adverse events (hospitalization or urgent outpatient visits for heart failure (HF)), along with diminished quality of life. Despite convincing data that evidenced-based, guideline-directed medical therapies (GDMT) improve mortality and heart failure-related events, there remains insufficient utilization of these life-saving drugs (evidence-based beta-blockers (EBBB), angiotensin-neprilysin inhibitors (ARNI)/ angiotensin converting enzyme inhibitors (ACEi)/ angiotensin receptor blockers (ARB), mineralocorticoid receptor antagonists (MRA) and sodium-glucose cotransporter 2 inhibitors (SGLT2i)) in patients with HFrEF.
- Objectives - The primary objective of this study is to implement and evaluate a multifaceted, interdisciplinary intervention to improve GDMT use, reduce mortality, and reduce future heart failure events in patients with HFrEF.
- Study Design – We will conduct a cluster-randomized controlled trial at the level of the clinician comparing two multi-faceted interventions to usual care with or without systemic education within a population of patients with HFrEF seen at a Geisinger cardiology clinic who are not on complete GDMT.
- Population - Patients at least 18 years of age with documented HFrEF or Left Ventricular Ejection Fraction (LVEF) < 40 (within two years prior to the triggering visit) who have an outpatient encounter with the Geisinger Cardiology department (office visit or telemedicine). Patients must also not currently be on optimal GDMT according to their electronic health records (EHR), as reflected in use of medications in fewer than four of the recommended classes or in all four classes but not ARNI. And patients must not currently be in hospice or palliative care or allergic to all non-prescribed GDMT. The clinician target population comprises clinicians practicing at one or more Geisinger outpatient cardiology clinics who manage care for patients with HFrEF and include cardiologists (MD/DO), nurse practitioners, and physician assistants.

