## 6. STUDY METHODS

### 6.1 Study Design

This is a cluster randomized study designed to evaluate the effectiveness of interventions aimed at improving GDMT in patients with HFrEF. Clinicians were stratified based on practice specialty, location, and pharmacist referral habits (see details below) and were permuted block randomized to achieve 45%/45%/10% proportional distribution across the following arms respectively: (1) usual care (**Control arm**); (2) multi-pronged CDS inclusive of a patient portal message about GDMT, an interruptive advisory upon chart entry advising clinicians of the need to optimize treatment, and a BPA that links to a GDMT order set

(**CDS-OS arm**); and (3) multi-pronged CDS as in #2 but replacing GDMT order set with referral to integrated clinical pharmacist co-management (**CDS-MTDM arm**). Secondarily, each of the 5 clinical practice sites of roughly equal HFrEF patient loads were assigned to receive either an early or delayed education rollout.

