#### 7.2.2 Approach for comparisons across intervention arms

*CDS analyses:* We will test whether each outcome differs as a function of each CDS active arm (CDS-OS and CDS-MTDM) relative to no-CDS control. Regressions will include as covariates education arm and interactions between CDS and education. We will retain both terms if the interaction is significant and retain the main effect if only it is significant. The education variable in CDS analyses will be coded as delayed education (baseline), early education, other (for clinicians who were not in the system early enough to be included in an education arm, to avoid either diluting or biasing the education effects).

As an exploratory analysis, we will compare CDS-MTDM against CDS-OS to see which is most effective.

Additionally, covariates will be added to exploratory versions of the final models as sensitivity analyses, to adjust for measured differences across clinicians, such as role, number of patients seen, and baseline rates of prescribing each of the GDMT classes. We have no *a priori* hypotheses about the moderating effects of these covariates.

*Education analyses:* We will test whether each outcome differs as a function of early education relative to delayed education. Regressions will include as covariates CDS arm and interactions between CDS and education. We will retain both terms if the interaction is significant and retain the main effect if only it is significant. Assignment to early versus delayed education is not random; therefore, regression analysis comparing education to no-education controls will adjust for as many relevant covariates as possible, including baseline prescribing rates.

In these analyses, we will exclude clinicians who were not present throughout the data collection period, beginning at assignment to early education. That is, we only intend to include clinicians in early and delayed education arms who theoretically could have been exposed to the education and who then had time to treat patients based on what they learned.

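### The baseline comparisons in section 7.2.1 use tests that treat patients as independent although clinicians were randomised, so their p-values will be too small for any characteristic that clusters by clinician (minor).

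*Combined protocol and SAP*

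**What the plan says.** The abstract fixes the unit of randomisation: "We will conduct a cluster-randomized controlled trial at the level of the clinician". Section 6.1 repeats it: "This is a cluster randomized study designed to evaluate the effectiveness of interventions aimed at improving GDMT in patients with HFrEF". Section 6.2 gives 155 clinicians (103 current and 52 hypothetical places for later joiners), allocated 45/45/10 to control, CDS-OS and CDS-MTDM. Section 7.1 gives the patient number: "Data will be collected from 4,300 patients assigned to the clinicians in the study".

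Section 7.2.1 opens: "Descriptive statistics will be computed for baseline socioeconomic and demographic characteristics". It names sex, age, race, ethnicity and insurance and leaves the list open. Differences across arms are to be tested: "t-tests will be used for continuous data, column proportion z tests or" chi-square, and "Mann-Whitney for non-normal quantitative data". It mentions no allowance for clustering. Section 7.2 sets the criterion, two-tailed p below 0.05, which "will be used to determine statistical significance in all analyses".

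Clustering is handled in two other places: the power statement (7.1) and the regression specification (7.2.3). The latter applies clinician-clustered robust standard errors to outcomes, other than timing of GDMT increases and ROI.

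**The concern.** Patients of one clinician share a clinic, a catchment area and a referral pattern, so characteristics such as race, insurance and age may be more alike within clinicians than between them. When clinicians are allocated, the chance variation of an arm mean depends on the spread between clinicians as well as between patients. A patient-level t, z, chi-square or Mann-Whitney test counts only the latter. Its standard error is too small, and it calls chance differences significant more often than its nominal rate.

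What is at stake is how the baseline table reads. A correctly randomised trial could show more significant differences than 5% testing should produce. The plan already recognises clustering of patients within clinicians for its outcomes, so the omission here is an internal inconsistency.

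**Working it through.** **The plan's own figure.** It states no error rate for the baseline tests, so there is nothing to reproduce directly. The nearest figure is in section 7.1: 80% power for about 5 points (CDS-OS) and 9 points (CDS-MTDM). It cannot be reproduced, because neither the control rate nor the ICC is given, but it can be inverted. With arms of 1,935, 1,935 and 430 patients (45/45/10 of 4,300), the design effect (DE) that leaves 80% power for a difference d is DE = [d / ((1.96 + 0.84) × SE)]², with SE the unclustered standard error. For assumed control rates of 10% to 50% this gives 1.24–2.83 (5 points) and 1.46–2.55 (9 points). So the power statement appears to allow for a material design effect in the outcome.

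**Inputs for the baseline tests.**
- Patients: 4,300 (7.1).
- Clinicians: 103 to 155 (6.2), so the mean cluster size m is 4,300/103 = 41.7 to 4,300/155 = 27.7.
- Nominal level: 0.05 two-tailed (7.2).
- ICC of each characteristic: not stated; assumed 0.001 to 0.05.
- Coefficient of variation (CV) of cluster size: not stated; assumed 0 to 0.7.

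**Formulas.** DE = 1 + (m(1 + CV²) − 1) × ICC. The actual two-sided rejection rate of an unadjusted test with no true difference is 2 × [1 − Φ(1.96/√DE)].

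**Worked example.** With 103 clinicians, equal sizes and ICC 0.01, DE = 1 + 40.7 × 0.01 = 1.41. Then 1.96/√1.41 = 1.65, and the rate is 9.9%. With CV 0.7 and ICC 0.05, DE = 1 + (41.7 × 1.49 − 1) × 0.05 = 4.06. Then 1.96/√4.06 = 0.97, and the rate is 33%.

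| ICC (assumed) | 155 clinicians, equal sizes | 103 clinicians, equal sizes | 103 clinicians, CV 0.7 |
|---|---|---|---|
| 0.001 | 5.3% | 5.5% | 5.7% |
| 0.005 | 6.6% | 7.4% | 8.6% |
| 0.01 | 8.2% | 9.9% | 12.3% |
| 0.02 | 11.4% | 14.6% | 18.9% |
| 0.05 | 20.0% | 26.1% | 33.1% |

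With equal cluster sizes, the rate doubles to 10% at ICC 0.010 (103 clinicians) or 0.016 (155). It triples to 15% at 0.021 or 0.032.

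**Check by simulation.** Clinicians were randomised 45/45/10 with no true difference, 1,000 runs per setting, CV 0 or 0.6. The t and z tests rejected in about 7–12% of runs at ICC 0.01, 10–20% at 0.02 and 19–32% at 0.05, in line with the formula. A clinician-clustered test on the same data rejected in about 4–7% for CDS-OS versus control and about 5–9% for CDS-MTDM versus control. The latter excess reflects the small number of clinicians in that arm (10% of 103 to 155, or about 10 to 16).

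**Cross-check against the power statement.** If baseline characteristics had the design effects of 1.24 to 2.83 derived above, the rejection rate would be about 8% to 24%. That is an analogy only, because outcome and baseline ICCs need not agree.

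**The case against.** The strongest reply is that the table is descriptive and nothing follows from it. This stands. Section 7.2.2 fixes education arm and its interaction with CDS as the covariates of the CDS models, with a retention rule based on their own significance. A reader might infer that false flags would steer the adjusted models, because section 7.2.2 also adds covariates "to adjust for measured differences across clinicians". The documents do not support that. Those covariates are exemplified by clinician-level factors (role, patient volume, baseline prescribing), they enter only exploratory sensitivity models, and no text makes their choice depend on a baseline p-value. The education models adjust because education was not randomly assigned, not because of a test result.

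A second reply is that inflation may be slight. This stands in part. A reader might conclude that false imbalances will appear several times more often than 5%. That needs an ICC of roughly 0.02–0.03 or more, or very unequal cluster sizes. It is plausible for characteristics tied to place, such as race or insurance, but is not shown for sex or age.

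Stratification by location among non-HF specialists (6.2) may also reduce between-arm variation. How far is unknown: 3 roles × 2 referral levels × 3 regions, plus 2 HF-specialist strata, make up to 20 strata for 103 current clinicians, and an exact 45/45/10 split needs blocks of at least 20 (9:9:2).

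A reader might also expect the problem mainly in the small CDS-MTDM arm. Simulated rates do not show this: at ICC 0.02 and CV 0.7, the unadjusted t-test rejected in 17.9% of runs for 46 v 10 clinicians and 18.5% for 46 v 46. A count of expected false flags cannot be given either, because section 7.2.1 leaves its list of variables open.

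Finally, section 7.2 allows alternative tests if assumptions fail. That clause concerns the outcome's distribution, with non-parametric tests as the example. Mann-Whitney assumes independence just as the t-test does, so the clause does not repair the omission.

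**Conclusion.** The point holds as a minor error in the plan as written. The direction is certain for any characteristic with a positive ICC by clinician. The size is not, because the documents give no ICC. Across formula and simulation, the false-positive rate is about 5% at ICC 0.001, 8–13% at 0.01, 10–20% at 0.02 and 19–33% at 0.05. These figures assume 4,300 patients, 103 to 155 clinicians and a cluster-size CV of 0 to 0.7, and make no allowance for stratification.

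The consequence is confined to the reported baseline comparisons. The figures describe the randomised CDS contrasts. Early versus delayed education was assigned by site and not at random, so a significant difference there need not be false.

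**What to change.** In section 7.2.1, replace the tests with standardised differences by arm, without p-values. This describes the size of any imbalance and needs no independence assumption to be read.

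If p-values are kept, use tests that account for clinician clustering, with a small-cluster correction for contrasts involving CDS-MTDM, because an uncorrected clustered test still rejected in about 5–9% of simulated runs there. State beside the education comparison that five sites were assigned, three early and two delayed, without randomisation. Clustering by clinician alone does not reflect that assignment.

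The cost is a few lines of SAP wording. No data collection, sample size or outcome analysis changes.
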